The Dose Expansion phase will commence following determination of the MTD/MAD and a review of the totality of safety data from Part 1. Part 2A will further characterize the safety profile of KZR-261 at the MTD or MAD and evaluate the anti-tumor activity of KZR-261 in subjects who have select malignancies. Up to 175 subjects may be enrolled in up to 4 tumor-specific cohorts (such as malignant melanoma [including uveal melanoma], mesothelioma, mCRPC, and mCRC) and 1 “All-Tumors” cohort. Additional or different tumor-specific cohorts may be investigated at the Sponsor’s discretion. Each tumor-specific cohort will enroll 15 subjects during Stage 1, expanding up to 35 subjects (Stage 2) as defined by a prespecified futility analysis and if the tumor type is not selected for investigation in Part 2B. If futility is not rejected after Stage 1 (ie, prespecified criteria for futility are met), subsequent enrollment to that Part 2A cohort will cease. The All-Tumors cohort may enroll up to 35 biopsy-evaluable subjects.

Part 2B: Dose Optimization

Dose optimization in tumor-specific cohorts may be initiated at the Sponsor's discretion based on the totality of data after the MTD/MAD has been determined. The Sponsor may also choose to cease enrollment in Part 2A and initiate enrollment of that tumor type in Part 2B. Approximately 30 subjects within each tumor-specific cohort will be randomized in a 1:1 ratio to receive KZR-261 at the MTD/MAD or a lower clinically active dose of KZR-261. Based on additional safety data from Part 2A, the Sponsor may convene an SRC meeting to determine whether a lower dose than the MTD/MAD as determined in Part 1 should be evaluated in Part 2B. Part 2B will further characterize the safety profile of KZR-261 to support determination of the RP2D and further evaluate the anti-tumor activity of KZR-261 in subjects with select malignancies. The number of tumor-specific cohorts to be investigated in Part 2B will be at the Sponsor's discretion.

Safety Review Committee (SRC)

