17. Disease that is measurable by standard imaging techniques according to RECIST v1.1 ([Eisenhauer et al., 2009](#)). For subjects with prior radiation therapy, measurable lesions must be outside of any prior radiation field(s), unless disease progression has been documented following radiation to the site.

Additional Inclusion Criteria for Parts 2A and 2B (Dose Expansion and Dose Optimization)

All subjects considered for enrollment into Part 2 of the study must meet the following criteria in addition to the criteria listed above.

18. Subjects who agree to submit fresh or archived tumor tissue must do so during the Screening period.
19. For subjects who have **cutaneous melanoma**
 - a. Must have histologic or cytologic evidence of disease that is locally advanced or metastatic (American Joint Committee on Cancer [AJCC] Stage 3 or 4).
 - b. Must have relapsed or be refractory to treatment with currently approved therapies, including an immune checkpoint inhibitor(s), or unable to tolerate approved therapy(ies).
 - c. For subjects with a RAF V600 mutation, the subject may have received therapy with a small molecule RAF V600 inhibitor with or without a small molecule MEK inhibitor.
20. For subjects who have **uveal melanoma**
 - a. Must have histologic or cytologic evidence of locally advanced unresectable or metastatic uveal melanoma.
 - b. Disease must be treatment naive or have progressed (radiologically or clinically) on most recent therapy.
21. For subjects who have **malignant mesothelioma of the peritoneum or pleura**
 - a. Must have histologic or cytologic evidence of malignant mesothelioma that is either metastatic or locally advanced and not amenable to surgical resection or treatment with localized therapies.
 - b. Must have been previously treated with an acceptable platinum-based regimen (eg, cisplatin or carboplatin combined with pemetrexed).
 - c. The subject may have received Tumor Treating Fields (TTFields).

- d. Has previously received treatment with an approved immunotherapy unless the subject is not a candidate for immunotherapy.

22. For subjects who have **mCRPC**

- a. Must have histologically or cytologically documented, locally advanced unresectable or metastatic adenocarcinoma of the prostate.
- b. Must have disease progression despite castration by orchiectomy or ongoing luteinizing hormone-releasing hormone (LHRH) analogue.
- c. Must have disease that progressed on or after treatment with androgen inhibitors.

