3.3. Part 2A: Dose Expansion

Following determination of the MTD/MAD, separate tumor-specific cohorts of subjects will be treated with KZR-261. For all subjects enrolled in a tumor-specific cohort, tumor biopsies (fresh [preferred] or archived) will be requested pre-treatment. For any subject who provides a tumor sample pre-treatment, an additional biopsy of accessible tumor tissue will be requested at either the end of Cycle 2 or at PD, whichever comes first. Pre-treatment tumor biopsies (fresh) will be required for subjects enrolled in the All-Tumors expansion cohort (exceptions to this requirement may be considered after discussion with the Medical Monitor); an additional biopsy of accessible tumor tissue will be required at either the end of Cycle 2 or at PD, whichever comes first.

Fifteen subjects will be enrolled in each tumor-specific cohort (Stage 1), which may be increased up to 35 subjects in total as determined by prespecified futility criteria in Stage 1 ([Section 10.6](#)) and if the tumor type is not selected for investigation in Part 2B. Up to 35 biopsy-evaluable subjects may be enrolled in the All-Tumors cohort.

The following distinct dose expansion cohorts may be evaluated, as depicted in [Figure 1](#).

Tumor-Specific Cohorts

- **Malignant melanoma**—histologically or cytologically confirmed, locally advanced unresectable or metastatic cutaneous or uveal melanomas ([Section 4.2](#)).
- **Malignant mesothelioma**—histologically or cytologically confirmed that is either metastatic or locally advanced and not amenable to surgical resection or local therapies ([Section 4.2](#)).
- **mCRPC**—histologically or cytologically confirmed, locally advanced unresectable or metastatic adenocarcinoma of the prostate that is castration (physical or chemical) resistant([Section 4.2](#)).
- **mCRC**—histologically or cytologically confirmed, metastatic or locally advanced unresectable colorectal carcinoma ([Section 4.2](#)).

All-Tumors Cohort

- **All-Tumors**—any relapsed or refractory solid tumors that are amenable to tumor biopsies ([Section 4.2](#)).

Additional (or different) tumor types may be investigated at the Sponsor's discretion in Part 2 if evidence of anti-tumor activity of KZR-261 during Part 1 or in the All-Tumors cohort in Part 2 supports further evaluation.

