4.2.1. Inclusion Criteria

1. Age \geq 18 years.
2. Willing and able to sign informed consent before initiation of any study-specific procedures or treatment.
3. Histologic or cytologic evidence of a malignant solid tumor (except primary central nervous system [CNS] neoplasms), either metastatic or locally advanced and not amenable to surgical resection or other locoregional therapies.
4. Disease that is resistant to or relapsed following available standard systemic therapy, or for which there is no standard systemic therapy, or refused such therapies if available.

Documentation of the reason must be provided for subjects who have not received a standard therapy likely to result in clinical benefit.

5. ECOG PS score of 0 or 1.
6. Adequate baseline hematologic function:
 - a. ANC $\geq 1.5 \times 10^9/L$. Myeloid growth factors must not have been administered within 7 days before the first dose of KZR-261.
 - b. Hemoglobin $\geq 8 \text{ g/dL}$ and no red blood cell (RBC) transfusions during the 14 days before the first dose of KZR-261.
 - c. PLT count $\geq 100 \times 10^9/L$ and no platelet transfusions during the 14 days before the first dose of KZR-261.
7. Adequate baseline organ function, as demonstrated by the following:
 - a. Serum creatinine $\leq 1.5 \times \text{ULN}$ (local institution) or calculated creatinine clearance $\geq 60 \text{ mL/min}$ by the Cockcroft-Gault formula.
 - b. Serum albumin $\geq 2.5 \text{ g/dL}$.
 - c. Bilirubin $\leq 1.5 \times \text{ULN}$ (local institution).
 - d. AST and ALT $\leq 2.5 \times \text{ULN}$ (local institution). Subjects with hepatic metastases may have ALT and AST $\leq 5 \times \text{ULN}$.
8. Serum amylase and lipase values $< 1.5 \times \text{ULN}$ (local institution).
9. FBS $< 200 \text{ mg/dL}$.
10. Fasting triglycerides $< 300 \text{ mg/dL}$.
11. International normalized ratio (INR) ≤ 1.5 or prothrombin time (PT) $\leq 1.5 \times \text{ULN}$ (local institution); and either partial thromboplastin time (PTT) or activated partial thromboplastin time (aPTT) $\leq 1.5 \times \text{ULN}$. Exceptions are allowed for patients receiving therapeutic anticoagulation for a history of thrombosis. Note: Anticoagulation with warfarin is exclusionary.

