10.1.3. Part 2B

In Part 2B (Dose Optimization), up to 120 subjects (30 per each tumor-specific cohort [15 per dose level]) may be enrolled into up to 4 tumor-specific cohorts based on the totality of data after the MTD/MAD has been determined. The sample size for Part 2B is based on clinical considerations.

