10.6. Interim Analyses

The Go/No-Go futility analysis for each tumor-specific cohort in Part 2A will be based on CBR as the primary outcome measurement (as defined in [Section 10.5.5](#)) after Stage 1 enrollment of 15 subjects. Each of the expansion cohorts is based on the following assumptions:

- Each expansion cohort has a maximum sample size of 35 with one interim futility analysis at 15 subjects. At the interim analysis, if there is 1 or no subject with CBR (ie, CBR rate <7%), further enrollment into the cohort will be stopped for futility. If futility is rejected at the interim analysis (ie, 2 or more of 15 subjects with clinical benefit), the final analysis will be based on a total 35 subjects (ie, 20 additional subjects evaluable for CBR). Note: Outcomes (ie, presence or absence of clinical benefit) for subjects enrolled in Part 1 with the same tumor type and who received the same dose of KZR-261 as evaluated in the corresponding Part 2A, tumor-specific cohort may be included among the initial 15 subjects at the interim analysis, as described above.

The operating characteristics of this design are presented in [Table 13](#). If the true CBR is less than 5%, there is a reasonable chance to reach the futility criterion at interim. On the other hand, if the true CBR is 20% or higher, the probability to stop for futility is moderately low (<20%).

Table 13: Operating Characteristics of Dose Expansion Phase (Part 2A)

True CBR	Interim Analysis (N=15)		Final Analysis (N=35)		
	Pr(Futility*)	Pr(obs. CBR ≥15% 6 or more subjects with CBR)	Pr(obs. CBR ≥20% 7 or more subjects with CBR)	Pr(obs. CBR ≥25% 9 or more subjects with CBR)	Pr(obs. CBR ≥25% 9 or more subjects with CBR)
5%	83%	<1%	<1%	<1%	<1%
10%	55%	11%	5%	<1%	<1%
15%	32%	39%	25%	7%	7%
20%	17%	67%	54%	25%	25%
25%	8%	86%	78%	52%	52%
30%	4%	95%	92%	76%	76%
35%	1%	98%	97%	91%	91%

CBR=clinical benefit rate; obs.=observed; Pr=probability

* 1 or fewer subjects with CBR among the first 15 subjects.

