### **7.4. Data Analysis Conventions**

All data analysis will be performed by [REDACTED] after the study is completed and the database has been locked. Statistical programming and analyses will be performed using SAS® version 9.4 or higher. Output will be provided in rich text format (RTF) for tables and portable document format (PDF) for tables, listings, and figures using landscape orientation. All study data will be listed by subject, dose level in Part 1 (Dose Escalation) and cohort in Part 2A and 2B (Tumor-Specific Dose Expansion and Dose Optimization), and visit (as applicable) based on all enrolled subjects unless otherwise specified. Listings will be sorted by dose level in Part 1 (Dose Escalation) and by cohort in Part 2A (Tumor-Specific Dose Expansion) and Part 2B (Dose Optimization), subject number, visit/time point, and parameter as applicable.

Summaries for continuous and ordinal variables will include the number of observations (n), arithmetic mean, standard deviation, median, minimum, and maximum. Minima and maxima will be reported with the same precision as the raw values; means and medians will be presented to one additional decimal place than reported in the raw values. Standard deviations will be presented to two additional decimal places than reported in the raw values. Summaries for discrete variables will include counts and percentages. All percentages will be rounded to one decimal place (ie, XX.X%). Changes from baseline will be calculated as follow-up visit minus baseline.

Unless otherwise specified, all data will be summarized by dose level and overall, for Part 1 (Dose Escalation), tumor-specific cohort for Part 2A (Dose Expansion), and dose and tumor-specific cohort for Part 2B (Dose Optimization).

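### The melanoma cohort pools cutaneous and uveal disease: Part 2B states no stratification by subtype and, separately, the Part 2A futility count is read without regard to subtype mix

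*Protocol*

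**What the plan says.** Protocol 3.3 defines a single melanoma cohort of "locally advanced unresectable or metastatic cutaneous or uveal melanomas". The two subtypes enter under different tumor-specific criteria (Protocol 4.2.2):

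- Cutaneous, criterion 19b: "Must have relapsed or be refractory to treatment with currently approved therapies, including an immune checkpoint inhibitor(s", or unable to tolerate approved therapy.
- Uveal, criterion 20b: "Disease must be treatment naive or have progressed (radiologically or clinically) on most recent therapy".

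General criterion 4 also applies to both: "Disease that is resistant to or relapsed following available standard systemic therapy, or for which there is no standard systemic therapy", or such therapy was refused. Protocol 1.2.2 describes uveal melanoma as a rare subset with limited treatment options. No quota for subtype is set.

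For Part 2B (Synopsis, Protocol 3.1 and 3.4) the allocation is: "Approximately 30 subjects within each tumor-specific cohort will be randomized in a 1:1 ratio to receive KZR-261 at the MTD/MAD", the alternative being a lower clinically active dose. No stratification factor or randomization method is given. SAP 3.1 repeats the 1:1 randomization. SAP 4.2.2 describes assignment without mentioning it, and SAP 4.3 says that all subjects are treated without randomization. On size, Protocol 10.1.3 says: "The sample size for Part 2B is based on clinical considerations".

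For Part 2A, Protocol 10.6 says: "The Go/No-Go futility analysis for each tumor-specific cohort in Part 2A will be based on CBR as the primary outcome measurement". Enrollment stops if 1 or fewer of the first 15 subjects has clinical benefit.

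Unless otherwise specified, SAP 7.4 summarizes data by tumor-specific cohort for Part 2A and by "dose and tumor-specific cohort for Part 2B (Dose Optimization"). Three provisions come close to subtype reporting. Protocol 10.5.5 allows tables of response, PFS and OS by malignancy if necessary. SAP 13.2.7 marks the primary diagnosis on the waterfall plot. SAP 9.2 lists the primary diagnosis and summarizes the anatomical location of the primary cancer.

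**The concern.** Subtype and prior treatment are plausible determinants of clinical benefit, and here they go together: uveal is the only tumor-specific group whose criteria expressly admit treatment-naive disease. Two things are at stake, and they are independent of each other.

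**(a) Part 2B.** With about 15 subjects per dose and no stratification, one dose may receive more uveal subjects than the other by chance. Part 2B supports the choice of the RP2D. Its efficacy contrast will be read descriptively, and without subtype tables an imbalance cannot be told apart from a dose effect.

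**(b) Part 2A.** One count of 15 gives a single stop-or-continue answer for two populations. If their CBRs differ, that answer depends on which subjects happened to enroll, and the reported CBR is a mixture whose weights were not planned.

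**Working it through.** **Inputs from the documents.** 15 per dose and 30 per Part 2B cohort (Protocol 10.1.3); stop at 1 or fewer of 15 (Protocol 10.6, SAP 5, footnote to Protocol Table 13). SAP 18 words the threshold as a CBR of at least 6.7% (1/15), which would put exactly one subject on the continue side; the rule in Protocol 10.6 and SAP 5 is used here.

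**Assumed inputs.** The documents give neither subtype CBRs nor the mix. Ranges are shown.

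**1. The plan's own figures.** Pr(stop) = (1−p)^15 + 15p(1−p)^14.

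- p = 5%: 0.463 + 0.366 = 82.9% (plan: 83%)
- p = 10%: 0.206 + 0.343 = 54.9% (plan: 55%)
- p = 20%: 0.035 + 0.132 = 16.7% (plan: 17%)
- p = 25%: 0.013 + 0.067 = 8.0% (plan: 8%)

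The other rows also reproduce.

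**2. Part 2B: chance of imbalance.** With K uveal subjects among 30 and 15 allocated to each dose, the uveal count at one dose is hypergeometric (30, K, 15).

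- K = 15: P(10:5 or worse) = 14.3%
- K = 10: P(7:3 or worse) = 24.5%; P(8:2 or worse) = 5.0%
- P(counts differ by 4 or more) for K = 6, 8, 10, 12, 15: 17%, 22%, 25%, 26%, 14%

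**3. Part 2B: size of the shift.** Shift = CBR gap × difference in uveal counts / 15.

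- Assumed CBR 5% uveal and 25% cutaneous, split 10:5: (10×0.05 + 5×0.25)/15 = 11.7% against (5×0.05 + 10×0.25)/15 = 18.3%, a difference of 6.7 points with no dose effect.
- A count difference of 4 gives 2.7, 4.0 or 5.3 points for a gap of 10, 15 or 20 points.
- With only 3 uveal subjects of 30, even a 3:0 split gives 0.20×3/15 = 4 points.

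**4. Part 2B: shift against sampling error.** Take K = 15 and CBRs of 5% and 25%.

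- Idealized perfect balance (7.5 uveal per dose): variance = 2×(7.5×0.05×0.95 + 7.5×0.25×0.75)/225 = 0.01567, SE = 12.5 points.
- Unstratified: the SD of the difference in uveal proportion is 0.186, so add (0.20×0.186)² = 0.00138. The total is 0.01705, SE = 13.1 points.
- For K = 10, the same steps give 13.7 points balanced and 14.1 points unstratified.

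The 6.7-point shift is therefore about half an SE (6.7/13.1 = 0.51).

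**5. Part 2A: stop probability by mix.** With m of 15 in the lower-CBR subtype, Pr(stop) = P(Bin(m, p_low) + Bin(15−m, p_high) ≤ 1).

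| m | 20% vs 10% | 25% vs 5% |
|---|---|---|
| 0 | 16.7% | 8.0% |
| 5 | 25.7% | 20.0% |
| 8 | 32.9% | 33.2% |
| 10 | 38.4% | 45.4% |
| 15 | 54.9% | 82.9% |

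The first and last rows are unmixed cohorts and match the plan's own table. Nothing in this step involves the Part 2B allocation.

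**The case against.** The case against has substance, and much of it stands.

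- **The Part 2B gain is small.** Even under a 20-point gap, ideal balance lowers the SE only from 13.1 to 12.5 points. The planned methods are exact intervals and Kaplan-Meier estimates, no test between doses is defined, and the RP2D rests on the totality of Parts 1 and 2. Melanoma enters Part 2B only if the Sponsor selects it.
- **The eligibility gap is narrower than 19b and 20b suggest.** Criterion 4 also binds uveal subjects. It does not close the gap, because a treatment-naive subject qualifies where no standard therapy exists or it was refused.
- **Other cohorts are mixed too**, for example mCRC by RAF V600 and MSI-H status and mesothelioma by site. That is fair, but only the uveal criterion expressly admits treatment-naive disease.

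Three stronger readings are tempting, and the documents do not support them.

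- A reader might infer that the missing stratification in Part 2B makes the futility decision depend on case mix. It does not: the futility rule belongs to single-arm Part 2A, and Part 2B has none.
- A reader might infer bias in the dose comparison. Randomization leaves chance imbalance centered on zero.
- A reader might infer that subtype is absent from the results altogether. The optional by-malignancy tables, the waterfall labels and the diagnosis listing give partial visibility. What is missing is any required CBR, ORR or PFS by subtype.

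**Conclusion.** The point holds as two separate, modest ones.

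(a) In Part 2B no stratification by melanoma subtype is stated. Material imbalance is fairly likely (14% for 10:5 or worse, 24.5% for 7:3 or worse, at the assumed mixes), but its effect on the dose contrast is about half an SE or less in the cases worked. Stratifying is worth doing because it is nearly free, not because the comparison fails without it. The contradiction between SAP 4.3 and the 1:1 randomization in SAP 3.1 and the protocol is plain and needs correcting in any case.

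(b) In Part 2A the pooled stop rule is sensitive to mix if CBR differs by subtype: 17% to 55% for 20% against 10%, and 8% to 83% for 25% against 5%. If the subtypes have the same CBR, the sensitivity disappears. The subtype CBRs and the mix are assumptions throughout.

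**What to change.** - **Protocol 3.4 and SAP 4.2.2:** stratify the Part 2B melanoma randomization by cutaneous versus uveal, and state the method. With blocks of 4 within stratum (an assumed choice), uveal counts would differ between doses by at most 2, a shift of at most 0.20×2/15 = 2.7 points for a 20-point gap.
- **SAP 4.3:** reconcile the statement that there is no randomization with SAP 3.1 and the protocol.
- **SAP 7.4 and 13:** present CBR, ORR and PFS by subtype within the melanoma cohort in Parts 2A and 2B.
- **SAP 18:** tabulate the Stage 1 clinical-benefit count by subtype next to the pooled count.

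The subtype tables make the mix visible to whoever reads the interim result. They leave the rule of 1 or fewer of 15, and its operating characteristics, unchanged. The cost is one binary stratification factor and one extra split in the efficacy tables, with small cells. No subjects or procedures are added.

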GLP	Good Laboratory Practice
HCC	hepatocellular carcinoma
HCO ₃	bicarbonate
hERG	human ether-à-go-go-related gene
HNSCC	head and neck squamous cell carcinoma
HNSTD	highest non-severely toxic dose
ICF	Informed Consent Form
ICH	International Council for Harmonisation
IEC	Independent Ethics Committee
INR	international normalized ratio
IP	investigational product
IRB	Institutional Review Board
IV	intravenous(ly)
LFT	liver function test
LHRH	luteinizing hormone-releasing hormone
mAb	monoclonal antibody
MAD	maximum administered dose
MCH	mean corpuscular hemoglobin
MCHC	mean corpuscular hemoglobin concentration
MCV	mean corpuscular volume
mCRC	metastatic colorectal carcinoma
mCRPC	metastatic castration-resistant prostate cancer
MedDRA	medical dictionary for regulatory activities
MRI	magnetic resonance imaging
MSI-H	microsatellite instability high
MTD	maximum tolerated dose
NCI CTCAE	National Cancer Institute Common Terminology Criteria for Adverse Events
ORR	objective response rate
OS	overall survival
PBMC	peripheral blood mononuclear cell

PCWG3	Prostate Cancer Working Group 3
PD	progressive disease
PD-1	programmed death receptor-1
PET	positron emission tomography
PFS	progression-free survival
PFS4	progression-free survival at 4 months
PFS6	progression-free survival at 6 months
PLT	platelet
PK	pharmacokinetic
PO ₄	phosphate
PR	partial response
PSA	prostate-specific antigen
PT	prothrombin time
PTT	partial thromboplastin time
QTc	corrected QT
QTcF	corrected QT by Fridericia's formula
RBC	red blood cell
RECIST	Response Evaluation Criteria in Solid Tumors
RP2D	recommended Phase 2 dose
SAE	serious adverse event
SRC	Safety Review Committee
STD ₁₀	severely toxic dose to 10% of animals
SUSAR	suspected unexpected serious adverse reaction
t _{1/2}	half-life
TCGA	The Cancer Genome Atlas
TTFields	Tumor Treating Fields
ULN	upper limit of normal
V _z	volume of distribution
VEGF	vascular endothelial growth factor
VEGFR2	vascular endothelial growth factor receptor-2
VS	vital signs
WBC	white blood cell
WOCBP	women of childbearing potential

